## PROTOCOL

Neurosteroids as Novel Therapeutic Agents for PTSD in OEF/OIF/OND Veterans

PI: [name], PhD

whether buildings are indoors or outdoors; or (3) 'Like/Dislike': whether the face is liked or disliked. This task probes emotion regulation: (1) implicit emotional processing, (2) attentional modulation of emotion, and (3) modulation of emotion by appraisal. The 'Gender' condition probes implicit emotional processing, as attention is focused on an emotional face while identifying its gender, and it is established that negative emotional faces induce negative emotions. The 'Inside/Outside' condition engages attentional modulation of emotion as in focusing attention on the building components superimposed on the emotional face. Attention modulation is recognized as a core component of emotion regulation. The 'Like/Dislike' condition engages cognitive appraisal of one's emotional/evaluative state and engaging appraisal increases activation of dorsal medial prefrontal cortex ([name] et al, 2000; Phan et al, 2004). Behavioral studies of emotional appraisal find that this strategy lowers distress (Lieberman et al, 2011). The ability of DHEA to impact functional connectivity between the amygdala and hippocampus in healthy volunteers undergoing the SEAT paradigm will be evaluated in Veterans with PTSD to an acute target engagement dose of DHEA (400 mg) and following a sustained 6-week treatment.

### **Risk/Benefit Assessment**

1. Human Participants Involvement and Characteristics Research participants will be recruited from Durham VA IRB-approved local advertising (flyers), Durham VA IRB-approved letters (and follow-up phone calls utilizing a Durham VA IRB-approved phone script), the VA Mid-Atlantic MIRECC Repository and Post-Deployment Mental Health Study (which currently contains 3,200 OEF/OIF/OND Veterans; over 94% of these Registry participants have already provided permission to be re-contacted for future research studies), and by referral from their Durham VA medical and behavioral health providers, for a target number of 40 randomized participants; of these 40 randomized participants, it is estimated that at least 32 participants will receive at least one study visit following randomization (20% drop-out assumed). We thus estimate that approximately 16 participants per group will be randomized to either adjunctive DHEA or placebo and will complete at least one study visit post-randomization; these 32 participants will thus be included in the modified intent-to-treat analyses.

Enrolled participants will 1) Be OEF/OIF/OND Veterans; 2) 18 – 65 years of age; 3) Have a diagnosis of PTSD as assessed using the CAPS-5 (minimum CAP-5 score  $\geq$  33); 4) Be on a stable medication regimen (no change in past 4 weeks); 5) Have no anticipated change in medications during study; 6) Only OEF/OIF/OND Veterans will be enrolled into this study; 7) No non-Veteran participants will be included; and 8) fully participate in the informed consent process.

2. Sources of Materials. All of the data for this study will be collected specifically for research purposes. All study data will be kept in a secured file to which only study investigators and study personnel will have access. Each participant will be assigned a

## PROTOCOL

Neurosteroids as Novel Therapeutic Agents for PTSD in OEF/OIF/OND Veterans

PI: [name], PhD

study number and all data and specimens will be identified by that study number. The list linking this number to participant identity will be kept in a file on a secure, password-protected computer to which only the Principal Investigator and study staff have access. Five sources of data will be maintained for this study and all collected information will be de-identified: a) the initial telephone screening, b) diagnostic interviews, c) physical examinations, d) psychiatric rating scales (both self-report and clinician administered, e) neurosteroid profiles and other laboratory measurements.

### 3. Potential Risks

a) *Physical Risk*: Physical risks associated with participation in this study include the risks of drawing blood and adverse effects from the study medication. Possible side effects from drawing blood include bruising, bleeding, or pain at the injection site, and (rarely) fainting and infection. Blood draws at each visit are minimal risk. In terms of the study medication, DHEA has been well-tolerated at doses up to 1,600mg per day over several weeks of administration. Side effects exceeding placebo that have occurred in previous clinical trials with DHEA have included mild acne, hirsutism, and decreased HDL levels. If a participant develops side effects at any dose, they may be brought down to the previously tolerated dose or they may be withdrawn from the study and, as by the PI or MD members of the research team (Drs. [name], [name], and [name]), referred for evaluation and treatment. We will perform laboratories at each study visit (Chem 7, CBC, GI Panel) and an ECG at study entry and completion. No serious adverse events have been reported to date utilizing DHEA (sold as a dietary supplement over-the-counter in the U.S.). Of note, participants will NOT be tapered from their current stable medication regimen; DHEA will only be “added on” to treatment-as-usual.

Similar to multiple prior investigations that have utilized at least the proposed dose and duration of DHEA administration in patients with psychiatric illness, it is important to obtain a personal and family history of breast, uterine, and prostate cancer in these individuals. For example, in the report by Bloch et al., 1999 published in *Biological Psychiatry* entitled "Dehydroepiandrosterone Treatment of Mid-Life Dysthymia" and Schmidt et al., 2005 published in *The American Journal of Psychiatry* entitled "Dehydroepiandrosterone Monotherapy in the Treatment of Midlife onset Major and Minor Depression" (conducted at the NIMH), men and women up to the age of 65 needed to be physically healthy and exclusion criteria included symptoms of prostatism, family history of breast cancer, and abnormal laboratory mammograms or gynecological examination findings. For our study, we thus plan to follow these same exclusionary criteria, specifically: 1.) Abnormally elevated PSA at screening will be exclusionary in males. In men below 50 years of age a serum value of PSA < 2.5 ng/ml is considered normal and will be exclusionary if greater than this value. Men 50 years and older having a serum PSA of greater than 4.0 ng/ml will be exclusionary. These are generally considered to be conservative values as PSA cut-off scores and will be used to guard against enrolling an individual than may have an undiagnosed prostate cancer. 2.) Female participants must have had a normal mammogram within the last year (if older

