### Design

This is a parallel-group, double-blind, placebo (PBO)-controlled, randomized Phase 2 pilot study using adjunctive dehydroxyepiandrosterone [DHEA (400 mg)] will be evaluated to establish Proof of Concept (POC) for this agent in OEF/OIF/OND Veterans with PTSD.

Aim 1. To determine the effects of an acute oral administration of adjunctive DHEA (400 mg) on neuroimaging measures of functional connectivity. We will conduct a parallel-group, double-blind, placebo (PBO)-controlled, randomized Phase 2 pilot study with one-time oral DHEA 400 mg in target engagement. To establish POC, we seek to determine if DHEA is superior to PBO in target engagement of neural circuits related to fear-anxiety-emotion regulation using the shifted-attention emotion appraisal (SEAT) paradigm (see below). Following a two-week placebo lead-in period (all participants), subjects will be randomized to receive a one-time oral dose of adjunctive DHEA (400mg) or PBO. Neuroimaging will occur 2 hours following drug administration for peak level effects on target engagement of fear-anxiety emotion circuit connectivity, as previously conducted by Sripada, [name], [name] et al.).

Primary Outcome Measure The primary outcome measure will be functional connectivity between amygdala-hippocampus assessed using fMRI based SEAT Paradigm as a target engagement endpoint. The fMRI based SEAT Paradigm has been previously validated to an acute administration of DHEA (400 mg) in healthy volunteers by members of my career development team, Drs. [name] and [name] (Sripada et al., 2013).

Aim 2. To evaluate a sustained 6-week adjunctive DHEA treatment compared to PBO on PTSD symptoms severity (CAPS-5), co-occurring depression (BDI), and other secondary outcome measures such as resilience (CD-RISC). Following randomization to acute DHEA administration or PBO the subject will continue to receive study drug for 6 weeks (for DHEA, fixed escalating doses: 100 mg per day in divided doses x 1 week, followed by 200 mg per day in divided doses x 1 week, followed by 400 mg per day in divided doses x 4 weeks).

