## PROTOCOL

Neurosteroids as Novel Therapeutic Agents for PTSD in OEF/OIF/OND Veterans

PI: [name], PhD

side effects during follow-up telephone phone calls (after study medication has been discontinued). Potential side effects will be monitored closely by the PI and MD members of the research team (Drs. [name], [name], and [name]). A participant may be asked to return for an unscheduled appointment to assess a potential side effect if clinically indicated.

**Laboratory Results:** Patients will receive a CBC, clinical chemistry panel, and GI panel at each study visit. Laboratory results that are outside of the normal range will be addressed by a member of the physician team. All labs will be reviewed by the study physician within 24 hours, and clinically relevant laboratory abnormalities will receive prompt follow-up attention. The Durham VA's Clinical Chemistry Laboratory will page the PI with any "alert" laboratory values that require immediate attention. Female patients will receive a serum pregnancy test. Male participants will receive a prostate specific antigen test (PSA).

**ECG Monitoring:** Final ECG readings issued by a cardiologist are available from the Durham VAMC Heart Station within 48 hours. Each patient will have an ECG at baseline and completion of the study. If the patient does not complete the study and withdraws prior to the final study visit, every effort will be made to obtain an ECG at the patient's last study visit. Any abnormal ECG findings will be discussed with a VA cardiologist by study physician ([name], [name], or [name]). If additional medical follow-up is suggested, we will proceed according to their recommendation. Additional potential follow-up actions may include, but are not limited to: Primary care provider notification by pager or email, the placement of a cardiology consult, a repeat ECG (if lead placement is suspected to have been suboptimal, for example), or referral to an onsite Acute Care Clinic/Emergency Department for assessment.

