### Schedule of Events:

Week	0	1	2	3	4	5	6	7	8	Follow up
Study Visit	1	Phone Call	2	Phone Call	3	Phone Call	4	Phone Call	5	Phone Call
Informed Consent	X									
Demographics, Medical History	X									
Mental Health Diagnosis	X									
Physical Exam and ECG	X								X	
Clinician Administered PTSD Scale	X		X		X		X		X	
Adverse Events		X	X	X	X	X	X	X	X	X
Mental/Physical Health Assessments	X		X		X		X		X	
Suicide Assessment	X	X	X	X	X	X	X	X	X	X
Blood draw and Vital Signs	X		X		X		X		X	
Urine Drug Test	X		X		X		X		X	
Urinalysis	X		X		X		X		X	
Urine Pregnancy Test	X		X		X		X		X	
Dispense Drug or Placebo	X		X		X		X		X	
MRI			X						X	

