### **Adverse Events**

This protocol presents minimal risks to participants. In the unlikely event than an adverse event occurs, serious and unanticipated and related adverse events or unanticipated problems involving risks to participants or others will be reported in writing within 48 hours to the IRB at the Durham VA Health Center and any appropriate funding and regulatory agencies. Adverse events will be recorded by administration of a side effect rating scale (Hillside Adverse Events Form) and reviewed by a study physician. Adverse events will be assessed at all study visits after the screening visit (i.e. Visits 2-5). In addition to receiving these regular adverse effect assessments, patients will be given a toll-free study number that they can call if they have questions regarding the dose escalation schedule or medication side effects. Participants will also be provided with the cell phone numbers of [name] and [name].

We will also summarize all adverse events (cumulative to date) in our reports to the FDA, Clinical Science Research & Development Central Data Monitoring Committee at Hines (CSR&D DMC), and annual request for continuing approval to the IRB. The principal investigator is responsible for monitoring the data, assuring protocol compliance, and conducting the safety reviews at intervals appropriate to the study. During the review process the principal investigator will evaluate whether the study should continue unchanged, require modification/amendment, continue or close to enrollment. Specifically, the principal investigator will assess whether the adverse event affects the Risk/Benefit ratio of the study and whether modifications to the protocol (at Risks to Subjects) or consent form (at Risk and Inconveniences) are required. The investigator will apprise fellow investigation and study personnel of all adverse events will be reported to the appropriate regulatory and oversight agencies in accordance with their reporting requirements and regulations.

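### Decreased HDL is listed as a DHEA side effect, but no named laboratory test measures it; unless an un-itemised panel does, the plan would not detect a fall

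*Combined protocol and SAP*

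**What the plan says.** Under Risk/Benefit Assessment, 3. Potential Risks, a) Physical Risk, the protocol names the effects it expects from DHEA: "Side effects exceeding placebo that have occurred in previous clinical trials with DHEA have included mild acne, hirsutism, and decreased HDL levels". The same paragraph sets out the response, "If a participant develops side effects at any dose, they may be brought down to the previously tolerated dose", with withdrawal as the alternative, and the monitoring: "We will perform laboratories at each study visit (Chem 7, CBC, GI Panel) and an ECG at study entry and completion".

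The Laboratory Results paragraph of the Safety Plan describes the panels slightly differently: "Patients will receive a CBC, clinical chemistry panel, and GI panel at each study visit". It adds a serum pregnancy test for women and PSA for men, and requires that "All labs will be reviewed by the study physician within 24 hours". The Schedule of Events has one row, "Blood draw and Vital Signs", marked at all five visits, and separate rows for urinalysis, urine drug test and urine pregnancy test. Data Analysis and Statistical Considerations adds three serum neurosteroids: DHEA, DHEAS and androsterone.

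For other side effects, the Adverse Events section says: "Adverse events will be recorded by administration of a side effect rating scale (Hillside Adverse Events Form) and reviewed by a study physician".

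**The concern.** The protocol itself treats a fall in HDL as a drug effect, yet the laboratory list in the same paragraph contains no test that would obviously show one. Acne and hirsutism can be seen on examination or reported by the participant. A change in HDL cannot.

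The plan's two safeguards, prompt physician review of laboratory results and dose reduction or withdrawal for side effects, both need a result to act on. Without an HDL value neither can work for this effect, and the safety reports to the FDA, the data monitoring committee and the IRB would carry no planned information on it. For other foreseen hazards the protocol does name a specific check: PSA with age-specific cut-offs, mammogram and pelvic examination, pregnancy tests, and a suicide severity scale at each visit.

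**Working it through.** The plan states no figure to reproduce. The check sets the listed effect against every laboratory test and safety procedure named in the text available for review.

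**Step 1. Named laboratory tests.**

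| Test | Where named | HDL or lipid test? |
|---|---|---|
| Chem 7 / clinical chemistry panel | Potential Risks; Laboratory Results | Not named as one; contents not listed |
| CBC | Potential Risks; Laboratory Results | No |
| GI panel | Potential Risks; Laboratory Results | Not named as one; contents not listed |
| PSA (men) | Laboratory Results | No |
| Pregnancy tests (serum, urine) | Laboratory Results; Schedule of Events | No |
| Urinalysis, urine drug test | Schedule of Events | No |
| DHEA, DHEAS, androsterone | Data Analysis and Statistical Considerations | No |

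Named tests that are an HDL or lipid test: 0. HDL is mentioned only in the sentence on side effects, and lipids and cholesterol are not mentioned. Two entries stay open because their contents are not given.

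**Step 2. Other procedures.** The side-effect form, vital signs, ECG and physical examination do not measure HDL. Medical chart review (Data and/or Specimen Acquisition) might turn up a value from routine care, but none is required.

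**Step 3. Size if neither panel includes HDL.** Forty participants are randomised to two groups in blocks of four, so about 40 / 2 = 20 per arm. Planned HDL values: 0 in each arm.

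**Step 4. When a value could still inform dosing.** Visits 1 to 5 fall at Weeks 0, 2, 4, 6 and 8. The placebo lead-in ends at Week 2. Aim 2 then gives 100 mg/day for 1 week (to Week 3), 200 mg/day for 1 week (to Week 4), "followed by 400 mg per day in divided doses x 4 weeks" (Weeks 4 to 8).

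- Visit 2 (Week 2): the last point before randomised drug, provided the sample precedes the dose. The neurosteroid analysis also takes its baseline after the lead-in.
- Visit 4 (Week 6): 6 − 4 = 2 weeks at 400 mg/day completed and 8 − 6 = 2 weeks left. A step down is still possible.
- Visit 5 (Week 8): on this reading, no randomised dosing is left for completers.

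The Schedule of Events also marks drug dispensing at Week 8, which this reading does not explain. The reference elsewhere to 8 weeks of drug or placebo fits 2 weeks of lead-in plus 6 of treatment. Neither changes the case for Week 6, which is on treatment either way.

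**Step 5. Assays needed.** At most 40 × 3 = 120. If all 40 have the Visit 2 sample and 32 attend both later visits (the plan's 20% drop-out), 40 + 32 + 32 = 104.

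**The case against.** The strongest objection is that the documents show only that two panels are not itemised. A reader might infer that HDL will certainly go unmeasured, and the text does not support that. The label Chem 7 makes HDL less likely in the chemistry panel, but the GI panel could contain it. This stands, and the point is conditional on it.

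A reader might also infer that participants are being exposed to an unmonitored harm. The documents do not show that either. They give no size or clinical consequence for an HDL change over 6 weeks, describe DHEA as well tolerated at up to 1,600 mg per day over several weeks, and exclude serious or unstable cardiovascular or metabolic illness. The trial also runs under an IND with reporting to the IRB, the data monitoring committee and the FDA. None of this measures HDL, but it limits the weight of the gap.

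Nor can the benefit of testing be expressed as DHEA exposure avoided. That would assume participants are stopped or stepped down because of HDL, and the plan gives no threshold, expected fall or probability of action.

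Finally, serum is stored at −80 degrees from every visit (Potential Difficulties and Limitations), so a by-arm comparison might be recovered later. The documents do not say whether consent or sample handling would allow an HDL assay, and a late result could not guide dosing.

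**Conclusion.** The point holds in conditional form. The protocol lists decreased HDL as a DHEA effect, none of its named laboratory tests is an HDL or lipid test, and no other planned procedure would show a fall. If neither the GI panel nor the clinical chemistry panel includes HDL, which is the more likely reading of the list as written, there would be no planned HDL value in either arm. If one of them does, the only defect is that the protocol does not say so.

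The priority is low. The primary imaging outcome, the CAPS-5 analysis and the other efficacy inferences are unaffected. The reason to act is that the effect is one the protocol itself lists and blood is already drawn at every visit.

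**What to change.** First, confirm what the GI and clinical chemistry panels contain and state it in Potential Risks and in Laboratory Results. If either includes HDL, that one sentence is the whole change.

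If neither does, add HDL or a lipid panel to the clinical blood already drawn at three points:

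- Visit 2, before the first randomised dose;
- Visit 4 (Week 6), while dose reduction is still possible;
- Week 8, or the last visit attended.

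Name the test in both sections, send results through the existing 24-hour physician review, and summarise change by arm descriptively. Any threshold for action is for the study physicians to set.

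The cost is at most 120 routine assays and a short amendment, with no extra visit or venipuncture. The one real downside is a small unblinding risk. Clinical coordinators administer the CAPS-5 and study staff review the electronic chart, so the amendment needs a stated procedure that keeps HDL results from the raters; the documents do not describe one at present. With about 20 participants per arm the by-arm summary should be read as descriptive only.

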## PROTOCOL

Neurosteroids as Novel Therapeutic Agents for PTSD in OEF/OIF/OND Veterans  
PI: [name], PhD

than 40), and 3.) Female participants must have had a normal pelvic exam in within the last year. The National Cancer Institute does not recommend screening for uterine cancers and the American Cancer Society advocates that at the time of menopause women should report any unexpected bleeding or spotting to their physician. Given that endometrial biopsy and transvaginal ultrasound are not appropriate screening methods according to the National Cancer Institute, during the screening interview for this study we will obtain a detailed history related to onset of menopause (if appropriate), and whether bleeding or spotting has occurred since then; unexpected bleeding or spotting will be exclusionary. This will help guard against placing a subject in the study that may have an undiagnosed uterine cancer.

b) *Emotional Distress*: Participants may potentially experience emotional distress as a result of participating in this study. The study procedures could potentially lead to emotional distress from discussing trauma histories during PTSD assessments. Being placed in an MRI machine can at times induce feeling associated with claustrophobia. Each participant will be closely monitored for emotional distress, suicidal ideation and homicidal ideation at screening and each study visit (the Columbia Suicide Severity Rating Scale) will be administered at each study visit). If a participant becomes significantly distressed or their psychiatric symptoms worsen and intervention is deemed appropriate, they will be walked to the emergency psychiatry clinic (on site) for evaluation and treatment (including potential hospitalization). The study medication will be discontinued and they will be withdrawn from the study if the patient is hospitalized, or if medical and/or psychiatric issues take precedence over study participation.

c) *Safety Plan*: We will implement a rigorous safety plan that encompasses close monitoring and care of medical issues in this study. The conduction of safety monitoring includes the following procedures outlined in the Physician On-Call Cascade. The FDA has issued an IND number #129,623 for the conduction of this study; once the study has been approved by the Durham VA IRB, we will enroll the first participant; we will follow all FDA guidelines for annual progress, adverse event, and other reporting procedures for this outpatient randomized control trial.

**Overview of Facilities:** The Durham VA Medical Center has acute psychiatric care available onsite 24 hours per day/7days per week provided by the Psychiatric Emergency Care (PEC) team, which is staffed by a Duke psychiatry resident, psychiatric social worker, and VA psychiatry attending. Should participants require immediate psychiatric care, they will be escorted to the PEC for further assessment and care. [name] is the PEC attending once a week.

**Vital Sign and Side Effect Monitoring:** Vital signs will be assessed at each study visit. Blood pressure greater than 160/95 will addressed by a study physician. If vital sign abnormalities require same-day medical follow-up, the patient will be assessed in the Durham VAMC Acute Care Clinic/Emergency Department. Patients will receive an extensive side effect scale at each study visit and will be queried regarding potential

